Patients will return to the ACTRI to complete session 7 and will follow the same procedures (except for drug administration) as Session 6. Participants must wait 2 days to participate but no longer than 7 days to complete Session 7. Drug symptomology will be assessed after each session.

Primary Outcome Measure(s):

1. Visual Analog Scale (VAS) and numerical rating scales (NRS): Pain ratings (VAS pain intensity, VAS unpleasantness, and numerical pain ratings) will be assessed in response to the straight leg raise test.
2. exploratory outcomes include those corresponding to "heat induced pain ratings" (i.e. thermal stimulation), and lying supine. The minimum rating ("0") is designated as "no pain" whereas the maximum ("10") is labeled as "most intense imaginable" or "most unpleasant imaginable." Higher numbers correspond to higher pain.
 - a. We will collect naloxone and saline induced changes in pain intensity and pain unpleasantness ratings

Sample Size Determination: Our targeted sample size is 60 cLBP patients (30/group). To conduct group comparisons among the two primary outcomes (naloxone + saline induced changes in pain intensity + unpleasantness) and to ensure an overall type I error rate < 0.05, we used conservative Bonferroni corrections ($p = .025$) in all power calculations. Employing the pilot data corresponding to our previous work (Wells et al., 2020), we fit repeated measures ANOVA models that include indicator

variables for group (mindfulness vs. sham) and drug (naloxone vs. saline). The estimated square root of mean square errors is 0.23 (23%) and 0.30 (30%) for pain intensity and pain unpleasantness, respectively. Thirty subjects will provide 80% power to detect a pain rating difference of 22% between the naloxone and saline conditions in the non-mindfulness group with an estimated SD of 0.3 (30%). We expect no meaningful differences in pain reductions between naloxone and saline infusion during mindfulness meditation. Thus, we will have 80% power to detect a significant group X drug type interaction. Finally, 30 subjects/group will provide 80% power to detect a significant group difference of 19% for pain intensity and 24% for pain unpleasantness. Such effect sizes parallel those observed in our pilot data (Wells et al., 2020). Statistical power will be also greater when pre-regimen pain ratings are entered as covariates to reduce residual variance.

Questionnaires for Study Assessments:

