Drug Administration: All studies will be conducted with the supervision of ACTRI nurses in the ACTRI. As previously conducted (Zeidan, Adler-Neal et al. 2016), a 0.15mg/kg bolus dose of naloxone (Naloxone HCl, Amphastar Pharmaceuticals) or 25ml of normal saline will be administered over 10 minutes via the IV line of the antecubital vein of the non-dominant arm. Onset of naloxone-induced opioidergic antagonism occurs within 2 min of infusion and exhibits an average half-life of 64 min (Ngai, Berkowitz et al. 1976). To further ensure that naloxone will antagonize opioid receptors for the study entirety, we will administer a supplementary maintenance intravenous infusion dose of 0.15 mg/kg/h naloxone or saline immediately after bolus infusion ceases. The duration of the study from the onset of IV infusion to completion will be no more than 25 (average time of infusion = approx. 15 minutes). Only the study physicians, research pharmacist, and study coordinator will be aware of participant drug assignment.

Sample Size Determination & Power:

Assuming a conservative 20% dropout rate, we will recruit and randomize a total of 74 cLBP patients (n=37/group) to a mindfulness meditation or non-mindfulness meditation regimen. To conduct group comparisons among the two primary outcomes (naloxone + saline induced changes in pain intensity + unpleasantness) and to ensure an overall type I error rate < 0.05, we used conservative Bonferroni corrections (p= .025) in all power calculations. Employing the pilot data corresponding to preliminary findings and our previous work [22], we fit repeated measures ANOVA models that include indicator variables for group (mindfulness vs. non-mindfulness), drug (naloxone vs. saline), and session order. The estimated square root of mean square errors is 0.23 and 0.30 for pain intensity and pain unpleasantness, respectively. Thirty participants per group will provide 80% power to detect a group difference of 0.19 for pain intensity and 0.24 for pain unpleasantness. Such effect sizes are consistent with those observed from our pilot data. Statistical power will be also greater when pre-regimen pain ratings are entered as covariates to reduce residual variance.

Data Analyses and Interpretation:

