**Title:** Chronic Low Back Pain and Meditation

**NCT Record #:** NCT04034004

**Date:** May 3, 2023

**PI:** [name]

**Sample Size Determination:** Our targeted sample size is 60 cLBP patients (30/group). To conduct group comparisons among the two primary outcomes (naloxone + saline induced changes in pain ratings) and to ensure an overall type I error rate  $< 0.05$ , we used conservative Bonferroni corrections in all power calculations. Employing the pilot data corresponding to our previous work (Wells et al., 2020), we fit repeated measures ANOVA models that include indicator variables for group (mindfulness vs. non-mindfulness) and session (baseline vs. naloxone vs. saline). The estimated square root of mean square errors is 0.23 (23%) for pain ratings. Thirty subjects will provide 80% power to detect a pain rating difference of 22% between the naloxone and saline conditions in the non-mindfulness group with an estimated SD of 0.3 (30%). We expect no meaningful differences in pain reductions between naloxone and saline infusion during mindfulness meditation. Thus, we will have 80% power to detect a significant group X drug type interaction. Finally, 30 subjects/group will provide 80% power to detect a significant group difference of 19% for pain intensity. Such effect sizes parallel those observed in our pilot data (Wells et al., 2020).

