#### Exploratory outcome

- SF-12 Health Survey (SF-12): This is a 12-item version of the SF-36 item Health Survey designed to assess general mental and physical functioning, and overall health-related quality of life.

**Statistical Analysis Plan:** To test the primary hypotheses, a 2 (group) X 2 (rest vs. manipulation) X 3 (baseline vs. naloxone vs. saline) mixed model ANOVA will be employed to test differences in the change in pain from supine to straight leg raise test (SLR 1; SLR 2) within and across each testing session. Significant interactions will be explored using post-hoc paired simple effects tests to test the hypotheses that non-mindfulness meditation but not mindfulness induced analgesia will be reversed by administration of naloxone but not saline. Between group comparisons will also be explored with simple effects tests.

Secondary and exploratory outcomes will be assessed with a 2 (group) X 2 (baseline vs. post-intervention) by testing between and within group differences comparing baseline vs. post-study assessments. Simple effects tests will interpret significant main effects and interactions.

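### The stated 80% power for the group-by-drug interaction does not follow from the 80% power stated for one group; with a common SD and alpha, at least one of the two figures is misstated

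*Protocol*

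**What the plan says.** The argument appears in the protocol (section 9, Sample Size Determination) and again in the SAP (Sample Size Determination). It has three steps.

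1. The one-group claim: "Thirty subjects will provide 80% power to detect a pain rating difference of 22% between the naloxone and saline conditions in the non-mindfulness group". The SD attached to this line is 0.3.
2. The expectation for the other group: "We expect no meaningful differences in pain reductions between naloxone and saline infusion during mindfulness meditation".
3. The conclusion drawn from these two: "Thus, we will have 80% power to detect a significant group X drug type interaction".

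On variability, the protocol says: "The estimated square root of mean square errors is 0.23 (23%) and 0.30 (30%) for pain intensity and pain unpleasantness, respectively". The SAP says only: "The estimated square root of mean square errors is 0.23 (23%) for pain ratings", yet it keeps the SD of 0.3 for the 22% line. Neither document says whether 0.3 is the SD of the paired naloxone-saline difference, the SD within each drug condition, or a residual SD from the pilot model. Neither gives a correlation between the two drug sessions.

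On alpha, the protocol sets 0.025 in both of its power sections. The second, Sample Size Determination & Power, reads: "we used conservative Bonferroni corrections (p= .025) in all power calculations". The SAP has "we used conservative Bonferroni corrections in all power calculations" without a value. Sidedness is not stated anywhere.

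The protocol's second power section repeats only the power for the group difference. It has neither the 22% line nor the interaction claim.

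**The concern.** The third step treats the interaction as if it had the same precision as the comparison within one group. A zero effect under mindfulness leaves the size of the contrast unchanged at 22%, but that zero must itself be estimated from 30 people, and its sampling error enters the interaction.

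The interaction is the direct, drug-specific test of whether naloxone acts differently under mindfulness and under the control. In the SAP's Statistical Analysis Plan, the naloxone comparisons within groups come after it: "Significant interactions will be explored using post-hoc paired simple effects tests". The protocol (Data Analyses and Interpretation) plans paired t-tests in each group without that condition. Because the investigators expect no naloxone effect under mindfulness, the interpretation depends partly on how null results are read. A reader told 80% would count a missed 22% interaction as a one-in-five event. If the one-group 80% is the firm figure, the drug-specific contrast would be missed about half the time.

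**Working it through.** **Inputs.** 30 analysed per group, a 0.22 difference in the non-mindfulness group, zero under mindfulness, an SD of 0.30, and RMSEs of 0.23 and 0.30 (protocol, Sample Size Determination). Alpha is 0.025 (protocol). Two assumptions are mine: two-sided tests, and equal SDs of the paired difference in the two groups.

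**Check of alpha and sidedness on the plan's group-difference lines.** With a two-sample noncentral t, SE = SD × √(2/30), 58 df, two-sided 0.025:

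- Intensity: 0.19 / (0.23 × √(2/30)) = 0.19 / 0.0594 = 3.20, power 81.3%.
- Unpleasantness: 0.24 / (0.30 × √(2/30)) = 0.24 / 0.0775 = 3.10, power 78.5%.

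These match the stated 80%. Two-sided 0.05 gives 88.2% and 86.1%. So two-sided 0.025 is the reading that fits those lines.

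**Formulas for the two claims.** Let s be the SD of a person's naloxone-saline difference.

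- One group: paired t, 29 df, critical value 2.364, noncentrality 0.22 / (s/√30).
- Interaction: two-sample t on the paired differences, 58 df, critical value 2.301, noncentrality (0.22 − 0) / (s × √(2/30)).

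The second noncentrality is the first divided by √2, whatever s is.

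**If the one-group 80% is exact.** Solving gives s = 0.374. One group: 0.22 / 0.0682 = 3.22, power 80.0%. Interaction: 0.22 / 0.0965 = 2.28, power 49.6%.

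**If the interaction 80% is exact.** Solving gives s = 0.270. Interaction: 0.22 / 0.0698 = 3.15, power 80.0%. One group: 0.22 / 0.0494 = 4.46, power 97.8%.

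**All readings at two-sided 0.025.** If 0.30 is the SD per condition and r is the between-session correlation, s = 0.30 × √(2(1 − r)). If an RMSE is the within-person residual SD, s = RMSE × √2.

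| s | Reading | One-group power | Interaction power | Interaction detectable at 80% |
|---|---|---|---|---|
| 0.270 | interaction 80% exact | 97.8% | 80.0% | 22.0% |
| 0.30 | 0.30 is the SD of the difference (or per condition, r = 0.5) | 94.5% | 70.4% | 24.4% |
| 0.325 | 0.23 × √2 | 90.3% | 62.6% | 26.5% |
| 0.374 | one-group 80% exact | 80.0% | 49.6% | 30.4% |
| 0.424 | 0.30 per condition, r = 0; or 0.30 × √2 | 68.3% | 39.1% | 34.5% |

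**Correlations implied if 0.30 is per condition.** r = 1 − s²/(2 × 0.09). The one-group 80% needs r = 0.22, and the interaction 80% needs r = 0.59. A higher assumed correlation raises the power further: r = 0.7 gives s = 0.232 and interaction power 91%, with one-group power 99.7%.

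**At uncorrected two-sided 0.05.** With s = 0.30 the interaction is 79.8% and the one-group power 97.3%. With s = 0.424 the one-group power is 78.4% and the interaction 50.6%. Each printed 80% can be recovered approximately, but under different SDs.

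**The case against.** **The stated interaction power may be right.** This stands. At 0.025 it is 80% or more if the SD of the difference is 0.270 or less. At uncorrected 0.05, with 0.30 as the SD of the difference, it is 79.8%. But then the one-group power is about 97% or more, and the one-group line is the misstated figure. The protocol also says that 0.025 was used throughout.

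**Both lines could mean at least 80%.** Read that way, an SD of the difference of 0.270 or less at 0.025 satisfies both. The incompatibility is between two figures of exactly 80% at equal SDs. The inference from one to the other still fails, because the first gives no information on whether the SD is that small.

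**The group SDs may differ.** With 0.374 in controls and half that (0.187) under mindfulness, SE = √((0.374² + 0.187²)/30) = 0.0763, the noncentrality is 2.88 and power is about 72%. Even with 0.10 under mindfulness it is 79%. The documents do not suggest such a difference.

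**Covariates will help.** The protocol says that adjusting for pre-regimen ratings will add power, without giving an amount. A covariate that is constant across the two drug sessions helps only as far as it predicts the within-person difference.

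**A reader might go further** and infer that the interaction power simply is 50%, or that it lies between fixed limits. The documents support neither. The 50% is conditional on the one-group line, and any upper limit reflects only where an assumed correlation is stopped. Nor does the one-in-two miss rate carry over to the SAP's own interaction test. That model has three session levels (baseline, naloxone, saline), and its 2-df group-by-session test depends on baseline gaps that the plan does not give.

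**Conclusion.** The inference is invalid in both documents, and with equal SDs the two powers cannot both be exactly 80% at a common SD and alpha. If the one-group 80% is exact, power for the 1-df interaction contrast is about 50% at two-sided 0.025. On the other readings of the printed SDs that need no between-session correlation above 0.5, it runs from 39% to 70%. It reaches 80% only with an SD of the difference of 0.270 or less.

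This rests on two-sided testing, equal SDs in the two groups, 30 analysed per group and a true effect of exactly zero under mindfulness. The documents show that at least one printed figure is misstated, but not which one. It should be corrected, as an error in the stated power. It does not show that the trial is too small.

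**What to change.** In the Sample Size Determination paragraph of both documents:

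1. Delete the sentence that infers the interaction power from the one-group power.
2. State from the pilot data what the 0.30 is: the SD of the paired difference, a per-condition SD (with the between-session correlation), or a residual SD.
3. Use alpha 0.025 on every power line, state the sidedness, and print the value in the SAP.
4. Restate the results from that one SD. Suggested text: *With 30 completers per group, two-sided alpha 0.025 and an SD of the naloxone-saline difference of [value], power is [x]% for a 22% difference within the non-mindfulness group and [y]% for a group-by-drug interaction of 22% versus 0%; the interaction detectable with 80% power is [z]%.*

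The last three columns of the table above supply x, y and z once the authors have settled the SD; another SD needs the same calculation.

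The cost is a paragraph in each document and possibly a less favourable stated power. No endpoint, test or sample size has to change.

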4. ESTIMATED DURATION OF THE STUDY

We estimate that the proposed study will take 5 years to complete. This includes completing data collection on 60 chronic low back pain patients, data analyses, and time for publication. Each participant will complete 7 study sessions, which includes review of medical records for confirmation of chronic low back pain, confirmation of study eligibility (i.e., positive response to the straight leg raise test, exclusion/inclusion criteria), baseline pain testing, four days of mental training (mindfulness/non-mindfulness) and two clinical visits where participants will be administered the straight leg raise test during placebo-saline or naloxone infusion. After all of the data has been collected, the investigators of the study will be unblinded and statistical analyses will be performed to test the study hypotheses at which point we will prepare the manuscript for publication.

We do expect recruitment to go smoothly and anticipate that data collection will be completed after 16 months which would provide ample time for data analyses and manuscript preparation.

With respect to the subject focused study procedures, a 4-subject cohort strategy would produce a start to finish accrual process of 1-2 months or less. An extra 2-3 weeks will be added to the schedule after one cohort completes to allow for the required accrual of the next group of 8 subjects. The total outside accrual boundary of this study, taking into account increased stringency with recruitment towards the end of the study and accounting for a 20% retention loss, is at an estimate of 12 months.

5. LAY LANGUAGE SUMMARY OR SYNOPSIS (no more than one paragraph)

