9. RESEARCH DESIGN AND METHODS

This proposed NIH-sponsored, randomized, and double-blinded psychophysical and pharmacologic study includes 7 separate study sessions. In this experiment, we are assessing if mindfulness reduces acutely evoked radicular pain in cLBP through endogenous opioids as compared to a validated (Zeidan, Johnson et al. 2010, Zeidan, Emerson et al. 2015), non-mindfulness meditation technique (non-mindfulness) by administering an opioid antagonist, naloxone, to determine if mindfulness based cLBP relief is mediated by endogenous opioidergic systems. Importantly, we are employing a well-validated, non-mindfulness meditation intervention as a placebo control. As previously (Zeidan, Johnson et al. 2010, Zeidan, Emerson et al. 2015), the non-mindfulness group will be instructed that they are in the "mindfulness meditation" intervention. Thus, we must blind non-mindfulness subjects to the nature of their respective intervention.

Each study session will be conducted on a separate day. All potential participants will be assessed for study eligibility at the pre-study screening and first study session. Participants will have 40 days to complete the study.

Exemption from 21 CFR 312.2(b)(iii): We and many other groups are exempt from key criterion outlined in 21 CFR 312.2(b)(iii) (The investigation does not involve a route of administration or dosage level or use in a patient population or other factor that significantly increases the risks (or decreases the acceptability of the risks) associated with the use of the drug product) because the dosage employed has been repeatedly demonstrated to be highly safe and effective at examining the study aims. This is demonstrated below and described in the attached IND Exempt supplement document (item 25).

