Non-mindfulness Meditation Training: The main purpose of the non-mindfulness meditation regimen is to serve as an active control for a crucial, essential element of mindfulness meditation (i.e., mindful attention to breath and non-reactivity to sensory events)(Zeidan, Johnson et al. 2010, Zeidan, Emerson et al. 2015). This regimen is designed so that the primary difference between the mindfulness and non-mindfulness meditation training is the mindfulness meditation group’s explicit mindfulness-based instructions (e.g., mindful attention to the breath). The non-mindfulness meditation group will be told that they are randomly assigned to the meditation group (Zeidan, Johnson et al. 2010, Zeidan, Emerson et al. 2015). In each of the four 20-minute training sessions, participants will be instructed to close their eyes, and to take a deep breath “as we sit here in meditation” every 2-3 minutes (Zeidan, Johnson et al. 2010, Zeidan, Emerson et al. 2015). All other aspects (training room, posture, facilitator, time providing instruction) of the non-mindfulness meditation intervention will be matched.

Sessions 6 & 7: Post-Regimen Session: We will employ a double-blinded crossover design to correspond to the administration of the opioid antagonist, naloxone and placebo-saline across two separate sessions at UCSD’s Altman Clinical and Translational Research Institute (ACTRI). A total of 30 subjects in each group will receive naloxone in Session 6 and saline in Session 7. Conversely, the other 30 subjects in each group will receive saline in Session 6 and naloxone in Session 7. After successful completion of their respective regimen, participants will report to the ACTRI. A research technician will greet patients as they arrive to the ACTRI and guide them to the clinic room. Next, the research technician will issue study assessments to the participant. ACTRI nurses will then administer an opiate-focused urine drug screening to confirm that no participants are using opioids to remove the risk of opioid withdrawal symptoms during naloxone administration, and a pregnancy test (if applicable). Weight will be subsequently measured to confirm the prescribed drug dosage. Next, the

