research technician will issue study assessments to the subject. We will recalibrate each participant's leg raise height/angle required to elicit a 2-point pain increase employing the methods described in Session 1. An ACTRI nurse will then insert the IV catheter into the non-dominant arm of each participant. As previously employed (Zeidan, Adler-Neal et al. 2016) for safety purposes, blood pressure, respiration, oxygen saturation, and heart rate will be systematically monitored/recorded. These sessions should take approximately 1.0 hour to complete.

Pre Rest + Heat: A thermal probe will be placed on the back of the "unaffected" calf while patients lie in the supine position. They will be instructed to "rest with your eyes closed" (~ 5 minutes). We will administer a "Heat" series that includes 10 alternating, 12-second plateaus of noxious (49°C) and 35°C stimulation. After completion, we will collect pain ratings.

Pre Rest + SLR: The procedures employed in Pre Rest + SLR will be matched to those employed in Session 1. Briefly, patients will lie in the supine position and be instructed to "rest with your eyes closed". VAS pain ratings will then be collected. With the aid of a technician, participants will then lift their legs to the angle/height calibrated to produce a 2-point VAS pain increase. After completion, we will collect pain ratings.

Bolus: An ACTRI nurse will then initiate the naloxone/saline bolus (based on weight) for approximately 8 minutes.

Pre Meditation + SLR: After completion of the bolus (~8 minutes), a study technician will aid participants to lift their legs to the height/angle calibrated to produce a 2-point VAS pain increase. Participants in the mindfulness and non-mindfulness meditation groups will then be instructed to "begin meditating until the end of the session" (Zeidan, Martucci et al. 2011, Zeidan, Emerson et al. 2015). An ACTRI nurse will then initiate the naloxone or placebo-saline infusion. After completion, we will collect pain ratings.

Post Meditation + Heat: A thermal probe will be placed on the back of the "unaffected" calf while patients lie in the supine position and during meditation. We will administer a "Heat" series that includes 10 alternating, 12-second plateaus of noxious (49°C) and 35°C stimulation. After completion, we will collect pain ratings.

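### Does letting study physicians and the coordinator know the drug assignment undo the double blind in Sessions 6 and 7?

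*Protocol*

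**What the plan says.** The Protocol introduces the study in section 9 as a "randomized, and double-blinded psychophysical and pharmacologic study includes 7 separate study sessions", and under Sessions 6 & 7 it states "We will employ a double-blinded crossover design to correspond to the administration of the opioid antagonist, naloxone and placebo-saline". Under Drug Administration in the same section it adds "Only the study physicians, research pharmacist, and study coordinator will be aware of participant drug assignment". Section 4 says "After all of the data has been collected, the investigators of the study will be unblinded", and then the analyses are run.

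The Sessions 6 & 7 text assigns some tasks by role. A research technician receives participants and issues assessments. Nurses do the urine screen, the IV line, the bolus and the infusion. For the leg raise after the bolus, "a study technician will aid participants to lift their legs to the height/angle calibrated to produce a 2-point VAS pain increase". Two tasks are described only in the first person plural. One is recalibrating the "leg raise height/angle required to elicit a 2-point pain increase employing the methods described in Session 1". The other is taking the ratings: "An ACTRI nurse will then initiate the naloxone or placebo-saline infusion. After completion, we will collect pain ratings". Session 7 repeats Session 6 apart from the drug.

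Recalibration is referred back to Session 1, where section 9 gives the leg-raise procedure to co-investigators and/or trained study staff. Section 14 (Naloxone) allows nursing staff and/or a physician to oversee procedures involving naloxone. The SAP does not discuss blinding.

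**The concern.** A study described as double-blinded normally keeps the people who elicit the outcome unaware of treatment. Here physicians and the coordinator know the drug as a matter of routine, and the plan does not say that they stay away from calibration or rating collection. The outcome is a spoken or marked pain score, and the hypothesis is directional: naloxone should reverse the analgesia of the non-mindfulness arm and leave that of the mindfulness arm alone. A person who knows both the infusion and the hypothesis could influence the score through tone or prompting. Randomising the drug order gives no protection, because such an influence follows the drug and not the session. The within-group naloxone-saline contrasts would take the full shift. Section 4 also appears to contradict Drug Administration if any study physician counts as an investigator.

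**Working it through.** **Who knows the drug, and who does what.** Setting the role assignments in the Protocol side by side:

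| Role | Drug-aware? | Tasks named in the Protocol |
|---|---|---|
| Study physicians | Yes | Confirm diagnosis (sections 9, 10); a physician evaluates prolonged pain (15) and may oversee naloxone procedures (14) |
| Research pharmacist | Yes | None in the session procedures |
| Study coordinator | Yes | Scheduling (9), enrolment and randomisation log (9, 16), recruitment contact (11) |
| Technicians | No, by the closed list | Assessments and leg lifts in Sessions 6 and 7 (9) |
| Nurses | No, by the closed list | Urine screen, IV line, bolus, infusion (9) |
| Not named | – | Rating collection; recalibration (Session 1 methods: co-investigators and/or trained staff) |

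(The table takes the coordinator titles used in sections 9, 11 and 16 to mean one role.) The drug-aware roles and the roles named in the Session 6 and 7 procedures do not overlap, apart from possible oversight by a physician, and overseeing is not rating. The sentence on the leg lift by a technician leads into the one on collecting ratings, so the natural reading is that the team in the room takes them.

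**What an influence would do if it occurred.** Within one group, let d be the true naloxone-saline difference. In session s (N or S), an angle error moves the leg-raise rating before the bolus by a_s and the one after it by r·a_s. Drug-aware prompting moves only the later rating, by b_s. The post-minus-pre contrast is then

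d + (r − 1)(a_N − a_S) + (b_N − b_S).

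- Angle: it is set before the bolus and used for both raises, so its term vanishes at r = 1 and is partly offset for r between 0 and 1. Recalibration is therefore the lesser issue.
- Prompting: b = b_N − b_S passes through in full.
- Group-by-drug interaction: the bias from prompting is b₁ − b₂ across the two groups, which is 0 if handling is the same in both.

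**Yardstick.** The Protocol and SAP power statements give 30 patients, 80% power, SD 0.30 and a target difference of 0.22. First, which reading of the SD gives 0.22? The detectable standardised effect for a two-sided paired t-test with n = 30 is 0.529 at alpha .05 and 0.589 at .025.

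- SD of paired differences 0.30: 0.529 × 0.30 = 0.159; 0.589 × 0.30 = 0.177. Neither is 0.22.
- Per-condition SD 0.30 with zero correlation, so SD of differences 0.30 × √2 = 0.424: 0.529 × 0.424 ≈ 0.225 at alpha .05; 0.589 × 0.424 ≈ 0.250 at .025.
- Independent samples of 30, alpha .05: 0.736 × 0.30 = 0.221.

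The 22% fits the second or third reading at alpha .05. With SD of differences 0.424 the standard error is 0.424/√30 = 0.0775. A shift reaches significance on its own at 2.045 × 0.0775 = 0.158 (alpha .05) or 2.364 × 0.0775 = 0.183 (alpha .025), about 16% and 18%. The other reading gives lower thresholds (2.045 × 0.0548 = 0.112; 2.364 × 0.0548 = 0.130) but does not return the plan's own target.

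**Route to a false conclusion.** The SAP runs the paired simple effects only after a significant interaction. A shift common to both groups leaves the group-by-drug interaction alone. It could still open that gate through the drug-by-manipulation term. The Protocol's paired t-tests have no such gate.

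**The case for a change.** The strongest case for acting is that no sentence keeps physicians or the coordinator away from the ratings, that a drug-aware physician may be in the room, and that the clinical coordinator also keeps the log in which group randomisation is tracked. If that is the study coordinator on the drug-aware list, one person knows group, drug and hypothesis. Handling could then differ by group and the interaction would no longer be protected. One sentence would close the gap, using staff already present.

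It stands that the plan does not write this down, and that if such a person took the ratings the bias could reach the main test. It does not stand that the plan arranges for this. The coordinator's named duties are scheduling, logging and recruitment, none of them in the infusion sessions. The restriction on drug knowledge is worded to limit it, and the double-blind label already commits the team to blind outcome collection. The sentence would record what the plan implies and would alter no estimate.

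The apparent conflict with section 4 depends on whether a study physician is an investigator. Section 15 refers to a team list in item 21, which is not in the public text, so the conflict cannot be established from it.

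**Conclusion.** The observation is accurate as far as it goes: three roles know the drug, and the plan does not name who collects ratings in Sessions 6 and 7. It shows no breach and no rule that would give a wrong result. The documents allow no estimate of bias; the 16% to 18% yardstick is a threshold and says nothing about whether any shift would occur. It assumes 30 patients per group, a per-condition SD of 30% and zero correlation between conditions.

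The conclusion rests on two assumptions: that ratings are taken by the technicians and nurses the plan puts in those sessions, and that the list of drug-aware roles is complete as worded. Both are the ordinary reading. Leaving the collector unnamed is a gap in detail that a competent team fills sensibly under a double-blind plan, so no change is called for.
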